it being supportive of the primary endpoint. BicrPFS is defined as the time from randomization to disease progression, according to RECIST v1.1 criteria as assessed by BICR, or death due to any cause, whichever occurs first. Only tumor scans prior to start of any subsequent anticancer treatment are included.

OS is defined as the time from randomization to death due to any cause.

Analyses of ORR will be performed in the subgroup of patients with measurable disease at baseline and will be summarized with frequencies and percentages. DOR will be tested as a stand-alone secondary endpoint, outside of the step-down procedure for multiplicity adjustment. DOR is defined as the interval from the first documentation of objective response (RECIST v1.1) to the earlier of the first documentation of disease progression (per RECIST v1.1) or death from any cause.

Safety Analyses

All safety analyses will be presented by randomized treatment group for all patients in the safety population (ie, all treated patients). Any patients enrolled in the open-label safety cohorts will be included in this safety analysis population.

Adverse events, clinical laboratory results, vital signs, ECOG performance status, body weight, and concomitant medications/procedures will be tabulated and summarized. Adverse events will be summarized overall and separately for serious adverse events (SAEs), AEs leading to discontinuation/treatment interruptions/dose reductions, AEs leading to death, and NCI CTCAE v5.0 Grade 3 or higher AEs. Body weight and vital signs will be summarized descriptively (N, mean, standard deviation, median, minimum, and maximum).

Independent Data Monitoring Committee

An IDMC will be established to review safety and efficacy data in compliance with a prospective charter. The IDMC will be comprised of oncologists with experience in treating women with ovarian cancer and a statistician, all of whom are not otherwise involved in the study as investigators.

The IDMC will:

- Review safety and efficacy of rucaparib and nivolumab compared with placebo, as well as the rucaparib + nivolumab combination compared to monotherapy to ensure the study is beneficial to patients.
- Ensure the study is conducted in a high-quality manner.
- Monitor the size of the tBRCA subgroup.

Results from the open-label safety cohort(s) will be shared with the IDMC.

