Rucaparib monotherapy for treatment of patients with advanced ovarian cancer in the maintenance setting demonstrated significant benefit of rucaparib compared to placebo across primary, secondary, and exploratory endpoints in the randomized, placebo-controlled Phase 3 study, Study CO-338-014 (ARIEL3).²³ In this study, investigator-assessed PFS (invPFS) was the primary efficacy endpoint, with PFS by BICR (bicrPFS) conducted as a key, stand-alone, secondary endpoint. Rucaparib maintenance treatment significantly improved PFS compared with placebo in all primary analysis groups of patients with recurrent ovarian cancer after a complete or partial response to platinum-based therapy (Table 1). Overall, rucaparib as maintenance treatment reduced the risk of progression or death by 63.5% (HR 0.365 [95% CI, 0.295-0.451]; p < 0.0001) in the ITT Population, demonstrating a strong treatment effect over placebo. Analysis of non-nested, non-overlapping patient subpopulations indicate that the significant improvement in PFS observed in the ITT Population was not driven only by the HRD or tBRCA (tumor tissue

deleterious alteration in BRCA1 or BRCA2) subpopulations. Nearly half (44.6%) of the ITT patients in the rucaparib group showed benefit at 1 year compared to 8.8% in the placebo group. At 18 and 24 months, 32.0% and 26.0%, respectively, of patients who received rucaparib were still progression-free compared to 5.8% and 2.6% in the placebo group. These investigator-assessed results were confirmed by results of BICR.

The ORR per RECIST v1.1, as assessed by the investigator, was analyzed in the subgroup of patients who had measurable disease (ie, measurable target lesions) at baseline. In the tBRCA population, the confirmed ORR was 15/40 (37.5%) for the rucaparib group and 2/23 (8.7%) for the placebo group (p = 0.0055). In the HRD population, the confirmed ORR was 23/85 (27.1%) for the rucaparib group and 3/41 (7.3%) for the placebo group (p = 0.0031), and in the ITT Population, the confirmed ORR was 26/141 (18.4%) for the rucaparib group and 5/66 (7.6%) for the placebo group (p = 0.0069).

Results of the exploratory endpoint of ORR, along with that of invPFS in the non-nested populations, demonstrated that rucaparib delayed disease recurrence and showed a further response to rucaparib treatment in patients with measurable disease in women with advanced ovarian cancer.

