## 3 GENERAL ANALYSIS CONVENTIONS

Efficacy analyses will be analyzed in the ITT Population as described in Section 10 below.

All safety analyses will be based on the Safety Population, which consists of all patients who received at least 1 dose of protocol-specified treatment of oral study drug and/or IV study drug. Further, for safety analyses, patients randomized to either arm containing IV Nivolumab (ie, Arm A or Arm C) who never receive Nivolumab, will be analyzed in the analogous arm containing IV Placebo (ie, Arm B or Arm D, respectively).

Quantitative variables will typically be summarized using frequencies and percentages for appropriate categorizations and may also be summarized using descriptive statistics. For variables summarized with descriptive statistics, the following will be presented: N, mean, standard deviation, median, minimum, and maximum. Categorical variables will be presented using frequencies and percentages.

The Kaplan-Meier methodology will be used to summarize time-to-event variables. The 50th (median) percentile with the 95% CI will be summarized for each randomized treatment group. The stratified hazard ratio from the Cox proportional hazards model will be used to estimate the HR between the randomized treatment groups. The number of patients with events and the number of censored patients will also be presented.

The primary endpoint of invPFS, secondary endpoint of OS, bicrPFS (if applicable), ORR and exploratory analyses for the ITT population will be analyzed using the stratification factors of HRD classification, disease status, and timing of surgery. If the model does not converge or if there are only patients from a single treatment arm per stratum or if one or more of the strata contain few patients (eg, <5 patients) then the stratification factor of disease status will be omitted first, then timing of surgery, if necessary. Additionally, the Firth correction in the PHREG procedure will be used.

All data will be used to the maximum possible extent but without any imputations for missing data.

Baseline is defined as the last measurement on or prior to the first day of oral study drug administration or randomization date if the patient was never treated.

Results of all statistical analysis will be presented using 95% CIs and two-sided p-values. The significance level for ATHENA-COMBO is set at a one-sided p=0.0125 (two-sided p=0.025).

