## 3.3 Statistical Hypothesis and treatment comparisons

The primary statistical hypothesis /objective of the ATHENA-COMBO comparison is to test for improvement in PFS for the combination of rucaparib and nivolumab over rucaparib monotherapy as follows:

- $H_0$ : HR (Arm A/Arm B)  $\geq 1$
- Ha: HR (Arm A /Arm B) < 1

In order to test the main hypothesis for ATHENA-COMBO, Arm A (oral rucaparib+IV nivolumab) will be compared against Arm B (oral rucaparib+IV placebo). All efficacy analyses will be tested at a one-sided 0.0125 level (two sided 0.025).

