## 10.2.4 Duration of Response by RECIST v1.1. as assessed by investigator

The Duration of Response (DOR) as assessed by investigator will be analyzed in the subgroup of patients who have a confirmed response by RECIST v1.1. DOR for any confirmed RECIST CR or PR will be measured from the date of the first response until the first date that progressive disease is documented. DOR will be calculated in months as the time from the first date of the scan showing a response to the first scan with disease progression +1 day. Any patients with an ongoing response will be censored at the date of the last post-baseline scan.

The DOR will be analyzed using Cox proportional hazard methodology and a log-rank test. In addition, a graphical presentation of DOR distributions, median DOR with 95% CI, and event rates will be presented.

Confidential 33 of 52

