## 10.2.4 Duration of Response by RECIST v1.1. as Assessed by Investigator

The DOR as assessed by investigator will be analyzed in the subgroup of patients who have a confirmed response (i.e., CR or PR) by RECIST v1.1 as described in Section 10.2.3. DOR will be calculated in months as the time from the first date of the scan showing a response to the first scan with disease progression +1 day. Any patients with an ongoing response will be censored at the date of the last post-baseline scan. Only tumor scans included for evaluation of the primary endpoint are considered for the DOR endpoint.

The DOR will be analyzed using Cox proportional hazards model and a log-rank test. In addition, a graphical presentation of DOR distributions, median DOR with 95% CI, and event rates will be presented.

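### Duration of response is compared by Cox model and log-rank test in responders only, so the hazard ratio and p-value have no randomised interpretation when response rates differ

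*SAP*

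**What the plan says.** COMBO SAP Section 3 sets a general rule: "Efficacy analyses will be analyzed in the ITT Population as described in Section 10 below". Section 10.2.4 departs from it. DOR "will be analyzed in the subgroup of patients who have a confirmed response by RECIST v1.1", and it "will be measured from the date of the first response until the first date that progressive disease is documented". The comparison follows: "The DOR will be analyzed using Cox proportional hazard methodology and a log-rank test". The same section also plans a graph of the DOR distributions, medians with 95% CI, and event rates. Section 3.3 places all COMBO efficacy analyses at one-sided 0.0125.

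MONO SAP Section 10.2.4 uses the same responder set and nearly the same sentence: "The DOR will be analyzed using Cox proportional hazards model and a log-rank test". Protocol Section 9.6.2.4 also restricts DOR to confirmed responders, and the protocol Synopsis (Secondary Efficacy Endpoints) says "DOR will be tested as a stand-alone secondary endpoint, outside of the step-down procedure for multiplicity adjustment".

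Neither SAP calls the DOR comparison descriptive or warns that it is not a randomised comparison. ORR, by contrast, is analysed in patients with measurable target lesions at baseline, a set fixed before treatment. (The COMBO SAP ends DOR at progression while the protocol ends it at progression or death; that is a separate matter.)

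**The concern.** Randomisation makes the arms comparable at baseline. It does not make the responders in each arm comparable, because treatment can change who responds. The plan itself treats response rate as a possible treatment effect: ORR is the last key secondary endpoint in the step-down. If Arm A produces responses in patients who would not have responded on Arm B, its responder group contains a kind of patient that Arm B's does not. A hazard ratio in that group can then move away from 1 even when no individual's response is lengthened or shortened.

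At stake is a reported HR and p-value, for a named secondary endpoint, that readers would take as a treatment effect on durability. In MONO there is a second, separate problem of precision: few placebo responders are likely.

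**Working it through.** The documents give no response rate, expected DOR, number with measurable disease, event count or power for DOR, so there is no planned figure to reproduce. The check is an illustration with assumed inputs.

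**1. Set-up (all assumed).** A share p = 0.20 of patients with measurable disease responds on either arm, with exponential DOR of median 12 months on both. A further share e responds only on Arm A, with median m. Censoring is uniform over 6 to 36 months. Treatment has no effect on duration in the shared responders.

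- Arm B responders: S_B(t) = 2^(-t/12).
- Arm A responders: S_A(t) = [p·2^(-t/12) + e·2^(-t/m)] / (p + e).

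**2. Median for e = 0.15, m = 6.** Put x = 2^(-t/12), so 2^(-t/6) = x². Then (0.20x + 0.15x²)/0.35 = 0.5, that is 3x² + 4x - 3.5 = 0. This gives x = (-4 + √58)/6 = 0.603 and t = 12·log2(1/0.603) = 8.8 months, against 12.0 on Arm B.

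**3. Large-sample Cox HR (A/B) in responders, and restricted mean time in response.** The mean is to 36 months over all patients with measurable disease, with non-responders scored 0. An exponential response of median m contributes (m/ln 2)(1 - 2^(-36/m)). Arm B: 0.20 × 17.31 × 0.875 = 3.03 months. For e = 0.15, m = 6, Arm A adds 0.15 × 8.66 × 0.984 = 1.28, giving 4.31.

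| Median of extra responses | HR, e = 0.10 | HR, e = 0.15 | Months in response, A (e = 0.10 / 0.15) | B |
|---|---|---|---|---|
| 6 | 1.24 | 1.32 | 3.88 / 4.31 | 3.03 |
| 8 | 1.14 | 1.18 | 4.13 / 4.68 | 3.03 |
| 12 | 1.00 | 1.00 | 4.54 / 5.30 | 3.03 |
| 18 | 0.88 | 0.84 | 4.98 / 5.95 | 3.03 |

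Simulated values vary around these limits (1.30 to 1.34 for the case listed as 1.32; 1.13 for the 1.14; 0.83 for the 0.84). In every row the effect on shared responders is nil, so each departure from 1.00 comes only from who is in the group. Values below 1 are as much a product of selection as values above 1.

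**4. When Arm A also lengthens shared responses.** Take 18.4% responding on B (the rucaparib rate in the earlier maintenance study), an HR of 0.90 in shared responders, extra responses of median 6 months, and censoring at 36 months. If Arm A's response rate is 25%, 30% or 37%, the responder-only HR is 1.08, 1.17 or 1.27. At 30%, mean time in response is 3.98 months on A and 2.79 on B, which ranks the arms correctly. With an assumed 80 measurable patients per arm, the estimated HR exceeds 1 in 55%, 66% and 75% of trials. Over 40 to 160 per arm, a significant result in the wrong direction (two-sided 0.025) occurs in about 1% to 8%. With equal response rates and the same responders, the HR returns the true 0.90 to within simulation error.

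**5. MONO numbers.** In the earlier rucaparib study (protocol Section 1.1.1.2.2.2), "the confirmed ORR was 26/141 (18.4%) for the rucaparib group and 5/66 (7.6%) for the placebo group", from 375 and 189 randomised patients (protocol Table 1). Scaling to ATHENA's 400:100 gives 400 × 26/375 = 28 rucaparib and 100 × 5/189 = 3 placebo responders. This assumes the same share with measurable disease and the same response rates. That study was in recurrent disease, so the figures are only a rough guide.

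**The case against.** The strongest reply is that the adverse cases depend on Arm A's extra responses being short, and the documents lean the other way. Protocol Sections 1.1.2.3.2 and 1.2 describe nivolumab responses as durable, including in ovarian cancer. With equally durable extra responses the HR is 1.0; with longer ones it falls below 1. A reader might infer that the better arm will show the worse hazard ratio. The documents do not support that: it needs both a higher response rate and shorter-lived extra responses, and nothing in them establishes the second. The cited evidence comes from other settings, however, and does not settle durability here. Nor does durability rescue the comparison, since an HR of 0.84 with no lengthened response is also misleading.

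Second, DOR carries no confirmatory weight. It is outside the step-down, and the COMBO SAP names an official test for invPFS, OS and ORR but none for DOR. This stands and limits the severity. It does not make the HR interpretable, because the fault is in the comparison and not in its multiplicity.

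Third, most of the descriptive output wanted is already planned. This also stands, and is why the change is small.

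Fourth, MONO is past the point of amendment. Version 2.0 of its SAP was signed on 10 February 2022, and COMBO SAP Section 3.5 records unblinding of Arms B and D on 23 March 2022. A reader might conclude that the analysis should be deleted from both SAPs; for MONO that would be a post-unblinding change to a pre-specified analysis.

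**Conclusion.** The point holds in a limited form. The plan produces a between-arm HR and p-value for DOR in a group selected by a post-randomisation outcome that treatment may change. Under the assumed inputs the distortion ranges from about 0.84 to 1.32 when the true effect on shared responders is nil. Its direction depends on how durable Arm A's extra responses are, which the documents do not give. With equal response rates and the same responders there is no distortion.

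A reader might infer that a confirmatory conclusion is in danger. It is not: DOR has no step-down alpha and cannot by itself support a formal claim. The risk is misreading of a reported secondary result. The change is worth making in COMBO; in MONO only the reporting needs care.

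**What to change.** **COMBO SAP, Section 10.2.4.** Drop the Cox and log-rank comparison of DOR. Keep the Kaplan-Meier curves, medians with 95% CI and event rates as descriptive output, and state that the responder groups are not a randomised comparison. Section 3.5 describes the sponsor team as still blinded to Arms A and C; make the change before the COMBO blind is broken. If it has been broken, handle COMBO as MONO below.

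**If a between-arm comparison is wanted,** use all randomised patients with measurable disease at baseline and compare restricted mean time in response, with non-responders scored 0. State that this combines response rate and duration, so it answers a different question from DOR.

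**Protocol Synopsis.** Change the verb for DOR from tested to summarised at the next amendment. An amendment needs ethics approval and regulatory submission (protocol Section 10.7), so this does not justify one on its own.

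**MONO.** Do not delete the pre-specified analysis. Report it as descriptive and non-randomised, give the number of responders per arm, and note that it may rest on few placebo responders.

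**Cost.** SAP wording, one optional table, and the loss of one unadjusted p-value. Sample size, step-down and data collection are unaffected.

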## **10.3** Exploratory Efficacy Analyses

The purpose of the exploratory endpoints is to further explore the efficacy; no multiple comparison adjustments are performed for these analyses.

## 10.3.1 PD-L1 Expression as Molecular Marker of Efficacy

The primary and secondary efficacy endpoints will be summarized by PD-L1 expression subgroups.

#### 10.3.1.1 PD-L1 Definitions

Definition of PD-L1 expression is described as follows.

• PD-L1 expression missing: Subjects without an available tumor biopsy specimen for PD-L1 evaluation will be considered as PD-L1 expression missing.

For subjects with an available tumor biopsy specimen(s), the following will be considered:

- PD-L1 expression is defined as the percent of tumor cell membrane staining in a minimum of 100 evaluable tumor cells per Dako PD-L1 IHC assay unless otherwise specified. This is referred to as *quantifiable PD-L1 expression*. If the PD-L1 staining could not be quantified, it is further classified as:
- Indeterminate: Tumor cell membrane staining hampered for reasons attributed to the biology of the tumor biopsy specimen and not because of improper sample preparation or handling
- Not evaluable: Tumor biopsy specimen was not optimally collected or prepared (eg, PD-L1 expression is neither quantifiable nor indeterminate)

**Baseline PD-L1 expression**: If more than one tumor biopsy specimen is available, baseline PD-L1 expression will be determined from the most recently collected specimen (prior to randomization) with a quantifiable result. If more than one baseline PD-L1 expression measurement is available at the same day for a subject, the highest baseline PD-L1 expression measurement will be used. If all specimens for a given subject are either indeterminate or not evaluable, then the PD-L1 expression will be considered indeterminate as long as at least one specimen is indeterminate. Otherwise, PD-L1 expression will be considered not evaluable.

PD-L1 status is a dichotomized variable using an X% cut-off for quantifiable PD-L1 expression. The PD-L1 positive immune cell score is determined by the % of tumor area that is covered by PD-L1 positive immune cells.

#### 10.3.1.2 Efficacy Analysis by PD-L1 expression

The primary and secondary efficacy endpoints will be analyzed using a pre-identified cutoff of PD-L1 positive immune cell score defined as  $\geq 5\%$  for the ATHENA study. Hence, an ATHENA patient will be classified as being PD-L1 high if the PD-L1 immune cell score in their tumor tissue sample is  $\geq 5\%$ . A secondary cut-off of PD-L1 positive immune cell

Confidential 34 of 52

score of  $\geq$ 1% will also be used for the ATHENA study. These cut-offs were selected based on results from the IMagyn050  study of an immune checkpoint inhibitor containing combination in front-line ovarian cancer that employed the PD-L1 SP142 assay and demonstrated improved clinical benefit in patients with a PD-L1 positive immune cell score of  $\geq$  5%. Additional cutoffs may be explored.

In addition, efficacy based on PD-L1 expression defined by the combined positive score (CPS) may be evaluated, including cut-offs of CPS  $\geq 1$  and CPS $\geq 10$ . CPS is the ratio of the number of all PD-L1-expressing cells (tumor cells, lymphocytes, macrophages) to the number of all tumor cells.

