7.3.1 Within 120 Days Prior to Randomization

Medical/oncology history, including demographic information (birth date, race, gender, etc.), smoking status, and oncology history, including date of diagnosis for epithelial ovarian, primary peritoneal, or fallopian tube cancer (and other malignancy, if applicable), prior surgeries/treatments received for cancer, dates of treatment

administration, best response achieved, radiology reports, and BRCA1/2 mutation status (if known);

- FFPE archival tumor tissue or screening biopsy sample. Sufficient archival FFPE tumor tissue (enough for 1 × 4 μm section for H&E and approximately 8 to 12 × 10 μm sections [unstained], or equivalent) is required for study participation per inclusion criteria #9. In addition to this minimum requirement, it is highly desirable to have additional 4 × 4 μm sections and 2 × 10 μm sections for other planned analyses. Refer to Section 7.5.7.1 for more information and to the central Laboratory Manual for detailed sample handling instructions.
 - Tumor tissue from the cytoreductive surgery must be provided.
 - Tumor tissue from a pre-treatment biopsy should be provided, if available, for patients treated with neoadjuvant chemotherapy (a core biopsy is preferred).
 - Submission of a tumor block preferred; if sections are provided, these must all be from the same tumor sample.
 - Tumor content ≥ 30% is strongly preferred for successful genomic scarring/LOH analysis. At a minimum, the tumor BRCA status is required. If LOH status is unknown in patients without BRCA mutations, enrollment is permitted, but attempts will be made to obtain additional tissue to enable an LOH result for final analysis.
 - Sample must be submitted to the central laboratory at least 3 weeks prior to planned start of treatment in order to enable stratification for randomization.
- AE monitoring (only record if related to screening procedures).

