7.5.7 Biomarker Analysis

7.5.7.1 Biomarker Analysis – Tumor Tissue

A sufficient quantity of tumor tissue from the cytoreductive surgery must be provided during the screening process and submitted to the central laboratory directly at least 3 weeks prior to the planned randomization for determination of HRD status. This tumor tissue is required for HRD stratification for randomization and for additional biomarker testing described below. If the patient received neoadjuvant chemotherapy, a pre-treatment core biopsy should also be provided, if available.

Sufficient quantity of tumor tissue must be confirmed by central laboratory testing in these patients during the study.

Sufficient archival FFPE tumor tissue (enough for $1 \times 4 \mu m$ section for H&E and approximately 8 to $12 \times 10 \mu m$ sections [unstained], or equivalent) is required for study participation per inclusion criteria #9. In addition to this minimum requirement, it is highly desirable to have an additional $4 \times 4 \mu m$ sections and $2 \times 10 \mu m$ sections for other planned analyses. In addition to determining HRD status, gene expression profiling on extracted RNA will be analyzed to classify tumors into gene expression molecular subtypes, which have been shown to associate with patient survival in HGSOC. Refer to the central Laboratory Manual for details. The tumor tissue sample must be of adequate quality (at least 20% tumor content [$\geq 30\%$ is strongly preferred] with a minimum of 80% nucleated cellular content), or a new sample must be acquired.

Optional pre-treatment core biopsies may be taken from patients who have measurable disease and disease that is accessible for biopsy, after chemotherapy is completed and prior to initiating study drug as outlined in this protocol.

A tumor tissue biopsy sample from the time of disease progression/randomized treatment discontinuation until the start of the next treatment is optional; patients must provide additional consent for this optional tumor tissue biopsy sample. If disease progression is caused by appearance of a new lesion(s), the lesion(s) should be prioritized for the optional biopsy. Detailed sample handling instructions are located in the central Laboratory Manual.

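### ATHENA-COMBO SAP 10.3.1.2 defines CPS without a scale factor, so at the protocol's 20% minimum tumour content (read as a share of cells) the CPS ≥ 10 cut-off cannot be met as written

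*SAP*

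**What the plan says.** ATHENA-COMBO SAP 10.3.1.2 bases its main PD-L1 analyses on the immune cell score, with a cut-off of 5% and a secondary cut-off of 1%. It then adds that "efficacy based on PD-L1 expression defined by the combined positive score (CPS) may be evaluated", naming cut-offs of CPS ≥ 1 and CPS ≥ 10. The definition follows: "CPS is the ratio of the number of all PD-L1-expressing cells (tumor cells, lymphocytes, macrophages) to the number of all tumor cells".

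The other PD-L1 measures carry their scale. In SAP 10.3.1.1, tumour-cell expression is the "percent of tumor cell membrane staining in a minimum of 100 evaluable tumor cells", and for immune cells: "The PD-L1 positive immune cell score is determined by the % of tumor area that is covered by PD-L1 positive immune cells". CPS has numerical cut-offs but no stated scale.

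On the tissue itself, Protocol 7.5.7.1 says: "The tumor tissue sample must be of adequate quality (at least 20% tumor content", with 30% or more strongly preferred. It describes the use of that tissue as follows: "This tumor tissue is required for HRD stratification for randomization and for additional biomarker testing described below". The same section goes on to include PD-L1 immunohistochemistry.

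**The concern.** A plain ratio of positive cells to tumour cells has a ceiling set by the tumour share of the specimen. With a minimum tumour share of one fifth, a cut-off of 10 looks out of range, which suggests that a scale factor was left out of the definition.

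PD-L1 expression as a molecular marker of efficacy is a listed exploratory objective (Protocol 2.3; SAP Table 1). If CPS were derived from cell counts as written, the ≥ 10 subgroup could not be populated under the conditions below, and the ≥ 1 subgroup would be selected on a far stricter rule than a scaled score would give. If the laboratory instead delivers a score that is already scaled, the SAP misdescribes the variable. In either case the sentence needs correcting.

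**Working it through.** The plan gives no sample size, power or expected prevalence for the CPS subgroups, so there is no figure of its own to reproduce. The check is an arithmetic bound.

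**Inputs**
- CPS as a plain ratio, with cut-offs 1 and 10: SAP 10.3.1.2.
- Tumour content of at least 20%, preferably 30%: Protocol 7.5.7.1.
- Assumption: tumour content means the tumour share of all cells, written t. The protocol does not say whether it means cells or area.

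**Step 1: ceiling of the plain ratio.** The ratio is largest when every cell in the specimen is PD-L1-positive, so the maximum is all cells / tumour cells = 1/t.
- t = 0.20: 1/0.20 = 5.0
- t = 0.30: 1/0.30 = 3.3
- t = 0.50: 1/0.50 = 2.0

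All are below 10. Reaching 10 needs t ≤ 0.10, and at t = 0.10 exactly it needs every cell positive. The bound is generous, because it treats every non-tumour cell as a lymphocyte or macrophage, the only non-tumour types that the SAP counts.

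**Step 2: what a plain ratio of 1 requires.** For a cut-off c, the PD-L1-positive share of all cells must be at least c × t. With c = 1 that is 20% of all cells at t = 0.20 and 30% at t = 0.30. If p is the positive share of tumour cells, the positive share needed among non-tumour cells is (1 − p) × t / (1 − t):

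| Tumour cells positive (p) | t = 0.20 | t = 0.30 |
|---|---|---|
| 0% | 25% | 43% |
| 50% | 12.5% | 21% |
| 100% | 0% | 0% |

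The cut-off of 1 is therefore attainable, and tumour cells alone satisfy it if all of them stain.

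**Step 3: illustration against the immune cell score.** Assume that the area share of positive immune cells equals their share of all cells. The plain ratio is then p + (immune share)/t. At an immune cell score of 5%, with p from 0 to 50%:
- t = 0.20: from 0.05/0.20 = 0.25 to 0.75
- t = 0.30: from 0.05/0.30 = 0.17 to 0.67

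Under this assumption, a patient exactly at the SAP's main PD-L1 cut-off would fall short of a plain ratio of 1 throughout that range.

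**Step 4: the same cut-offs with a factor of 100.** The PD-L1-positive share of all cells needed becomes c × t / 100:
- t = 0.20: 0.2% for CPS ≥ 1 and 2% for CPS ≥ 10
- t = 0.30: 0.3% for CPS ≥ 1 and 3% for CPS ≥ 10

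Both cut-offs are then within reach.

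**The case against.** The strongest reply is that this is an editorial gap in an optional analysis. CPS only may be evaluated, and SAP 10.3 applies no multiplicity adjustment to exploratory analyses. PD-L1 positivity is defined through the immune cell score, so the PD-L1 objective can be met without CPS. SAP 6.3 has PD-L1 tested by an external laboratory, and the sentence may merely describe a score that arrives already scaled. All of this stands, and it limits the importance of the point.

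The ceiling of 5 is also conditional. If tumour content is measured by area, the cell share could be lower and the cap is not strict. The 20% minimum is set where the protocol describes tissue from cytoreductive surgery, and Protocol 7.3.1 says of the 30% level that it "is strongly preferred for successful genomic scarring/LOH analysis". SAP 10.3.1.1 takes baseline PD-L1 from the most recently collected quantifiable specimen before randomization. Protocol 7.3.2 allows optional core biopsies after chemotherapy, to which the 20% limit is not clearly applied. The SAP's own requirement of 100 evaluable tumour cells sets a count and does not cap the ratio. These conditions stand too.

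They do not remove the problem: the text as written pairs an unscaled ratio with a cut-off of 10, and nothing elsewhere in the documents supplies the scale.

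**Conclusion.** The point holds as a minor error in a derivation rule. Provided that tumour content is a share of cells and the scored specimen has at least 20%, the ratio as defined cannot exceed 5 and the CPS ≥ 10 subgroup cannot be populated. CPS ≥ 1 is strict but attainable.

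A reader might infer more than the documents support:
- **That CPS ≥ 1 would be almost empty.** No distribution of tumour-cell or immune-cell staining is given, so the number of patients cannot be computed.
- **That none of the roughly 800 patients in Arms A and B could reach 10.** This depends on both conditions above holding for every scored specimen, which the documents do not establish.
- **That the cut-offs are exactly 100 times too high.** No factor of 100 appears in the documents. It is a scale that makes both cut-offs workable, and it needs confirmation.
- **That the report would wrongly call the population CPS-negative.** The documents do not say who computes CPS or on what scale, and an empty subgroup would be visible at first output.

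The 5% and 1% immune-cell-score subgroups, the primary analysis and all alpha-controlled tests are unaffected.

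**What to change.** In ATHENA-COMBO SAP 10.3.1.2, state the scale in one of two ways:
- define CPS = 100 × (number of PD-L1-expressing tumour cells, lymphocytes and macrophages) / (number of all tumour cells), and keep the cut-offs of 1 and 10; or
- keep the plain ratio and restate the cut-offs on that scale (0.01 and 0.10 would be equivalent to the first option).

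Before finalising, confirm with the testing laboratory which scale its reported score uses, and make the SAP text match. The cost is one line of SAP text and one query to the laboratory. No new data are needed, and no other analysis changes.
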